4.2.1.4 Supplementary Analyses of the Primary Endpoint

Not applicable.

4.2.2 Secondary Endpoints

4.2.2.1 Secondary Endpoint-1

The ACQ-5 is a shortened version of the full 7-item ACQ (Juniper et al 1999) that assesses asthma symptoms (night-time awakening, symptoms on awakening, activity limitation, shortness of breath, and wheezing) but omits the FEV1 measurement and SABA use from the original ACQ assessment. Patients are asked to recall how their asthma has been during the previous week by responding to 5 symptom questions. Questions are weighted equally and scored from 0 (totally controlled) to 6 (severely uncontrolled). The mean ACQ-5 score is the mean of the responses. Mean scores of ≤ 0.75 indicate well controlled asthma, scores between >0.75 and <1.5 indicate partly controlled asthma, and a score ≥ 1.5 indicates not well controlled asthma (Juniper et al 2006). Individual changes of ≥ 0.5 are considered to be clinically meaningful (Juniper et al 2005).

The change from baseline in the proportion of well-controlled asthma evaluated by ACQ-5 score at week 48 will be derived using the percentage of patients with ACQ-5 score ≤ 0.75 , its 95% confidence interval (95% CI) will be summarized descriptively. Normal approximation method will be used to calculate 95% CI.

Distribution of ACQ-5 average scores at baseline and weeks 12, 24, 36 and 48 will be described as summary and listing, using the frequency and percentage at each category listed below, a shift table will also be generated:

- Well controlled: $ACQ-5 \leq 0.75$
- Partly controlled: $0.75 < ACQ-5 < 1.5$
- Not well-controlled: $ACQ-5 \geq 1.5$

4.2.2.2 Secondary Endpoint-2

One secondary endpoint is the proportion of patients on the treatment of ICS-formoterol as reliever, without concomitant SABA. Change from baseline in the proportion of patients on the treatment of ICS-formoterol as reliever at week 12, 24, 36 and 48 will be summarized with its 95% confidence interval (95% CI). Normal approximation method will be used to calculate 95% CI. Doctor's prescription will be used to define this endpoint. The baseline and following analysis visits' definitions refer to section 4.1.9.

4.2.2.3 Secondary Endpoint-3

The ACQ-5 overall score will be calculated as the average of the non-missing 5 symptom questions. At least 4 out of the 5 symptom items are needed to provide an ACQ-5 overall score. Change from baseline in ACQ-5 average score at week 12, 24, 36 and 48 will be summarized.

Responder status will be descriptively summarized by visit as the number (%) of responders and non-responders. A responder status at post-baseline will be calculated as

- Responder: $(\text{post-baseline} - \text{baseline}) \leq -0.5$
- Non-responder: $(\text{post-baseline} - \text{baseline}) > -0.5$

Proportion of participants achieving an improvement in ACQ-5 MCID of 0.5 units or more at Week 12, 24, 36 and 48 will be summarized.

4.2.2.4 Secondary Endpoint-4

Change from baseline in the proportion of patients with an ICS-based maintenance and/or reliever treatment at week 12, 24 and 36 will be summarized with its 95% confidence interval (95% CI). Normal approximation method will be used to calculate 95% CI.

4.2.2.5 Secondary Endpoint-5

Asthma related treatment patterns will be evaluated by treatment distribution at baseline and at weeks of 12, 24, 36 and 48, e.g., ICS-containing medications, ICS-LABA, SABA, ICS-formoterol, oral corticosteroids, leukotriene receptor antagonists, theophylline, Traditional Chinese Medicine and combination.

4.2.3 Other Endpoint

4.2.3.1 Exploratory Endpoint-1

4.2.3.2 Exploratory Endpoint-2

4.2.3.3 Exploratory Endpoint-3

4.2.3.4 Exploratory Endpoint-4

4.2.3.5 Exploratory Endpoint-5

4.2.3.6 Exploratory Endpoint-6

4.2.3.7 Exploratory Endpoint-7

4.2.3.8 Exploratory Endpoint-8

4.2.3.9 Exploratory Endpoint-9

4.2.3.10 Exploratory Endpoint-10

4.2.3.11 Exploratory Endpoint-11

4.2.3.12 Exploratory Endpoint-12

4.2.3.13 Exploratory endpoint-13

4.2.4 Subgroup analyses

Subgroup analyses as below will be performed as appropriate for the primary endpoint, selected secondary endpoints and exploratory endpoints. Any subjects with a missing value for the defined subgroup will be excluded from the analysis of that subgroup. The subgroups to be explored may include as needed:

- Age by category: >65 years, ≥ 18 to ≤ 65 years, <18 years old
- Age of onset: <20 years old, <40 years old, ≥ 40 years old
- Phenotype of asthma: allergic or non-allergic
- Hospital Tier: Tier 2, Tier 3
- Job: related to asthma, no-related to asthma (occupational exposure Y or N)
- Nicotine usage frequency (current, former, never)
- Sex (Male, Female)

- BMI ($\geq 24 \text{ kg/m}^2$, $< 24 \text{ kg/m}^2$)
- Education level (elementary school and below, high school, university degree and postgraduate)
- Questionnaire with response and non-response subjects (if the subject performed ACQ and AQLQ at Visit 5 and had any questionnaire performed in each visit, the subject is defined as responder; otherwise, the subject is a non-response subject)
- Adherence (Good adherence or not)
- Patient expectation of asthma treatment
- Asthma severity class: Mild, Moderate, Severe (based on Patient Self-Assessment of Asthma Severity)
- Symptoms: Symptoms less than twice a month; Symptoms twice a month or more, but less than 4-5 days a week; Symptoms most days, or waking with asthma once a week or more; Daily symptoms, or waking with asthma once a week or more, and low lung function
- Hospital Type: PCCM, non-PCCM
- Geographic region: North, South
- ICS containing change: with-to-with, with-to-without, without-to-with, without-to-without ICS containing (From ICS containing to ICS containing, from ICS containing to no-ICS-containing, from no-ICS-containing to ICS-containing, from no-ICS containing to no-ICS-containing.)
- ICS-formoterol as reliever: with-to-with, with-to-without, without-to-with, without-to-without ICS-formoterol as reliever (From ICS-formoterol as reliever to ICS-formoterol as reliever, from ICS-formoterol as reliever to no-ICS-formoterol as reliever, from no-ICS-formoterol as reliever to ICS-formoterol as reliever, from no-ICS-formoterol as reliever to no-ICS-formoterol as reliever.)
- Participants complete status: Missing at Week 24, not Missing at Week 24.
- Participants complete status: Missing at Week 48, not Missing at Week 48.

These analyses are exploratory and the result from these subgroup analyses will not affect the choice of the model for the primary analysis.

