4.2.1 Primary Endpoint

4.2.1.1 Definition

The primary endpoint is the proportion of patients with an ICS-based maintenance and/or reliever treatment, which is indicated by whether or not the treatment option includes ICS-containing medication. Change from baseline in the proportion of patients with an ICS-based maintenance and/or reliever treatment at week 48 will be analysed.

Doctor's prescription will be used to define this endpoint. The baseline and following analysis visits' definitions refer to section 4.1.9.

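### Age-of-onset subgroups overlap, and the shared subgroup list offers the primary endpoint groups that are defined by its own outcome or by having no week-48 value

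*SAP*

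**What the plan says.** SAP section 4.2.4 gives one subgroup list for several classes of endpoint: "Subgroup analyses as below will be performed as appropriate for the primary endpoint, selected secondary endpoints and exploratory endpoints". It opens the list in permissive terms, "The subgroups to be explored may include as needed", and calls the analyses exploratory. It does not say which subgroup belongs to which endpoint.

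Four entries matter here:

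- Age of onset: "Age of onset: <20 years old, <40 years old", followed by a third band of 40 years or older. Protocol section 9.4.3 has the same three bands.
- ICS change: "ICS containing change: with-to-with, with-to-without, without-to-with, without-to-without ICS containing". No timepoints are given for the change. Protocol section 9.4.3 has the same entry.
- Reliever change: "ICS-formoterol as reliever: with-to-with, with-to-without, without-to-with, without-to-without ICS-formoterol as reliever". This too is in both documents, and again without timepoints.
- Completion status: "Participants complete status: Missing at Week 48, not Missing at Week 48". Protocol section 9.4.3 introduces this entry separately, as a way to describe the characteristics of missing data. The SAP places it in the general list without that introduction.

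SAP section 4.2.1.1 defines the primary endpoint by a yes/no variable, "which is indicated by whether or not the treatment option includes ICS-containing medication", and states the contrast: "Change from baseline in the proportion of patients with an ICS-based maintenance and/or reliever treatment at week 48 will be analysed". SAP section 3.1.7 says that missing data are not imputed unless the SAP specifies otherwise.

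**The concern.** Subgroup rows are normally read against one another. That needs rows that do not share patients, a grouping variable that is not the outcome itself, and an outcome that exists in every row. Each entry above breaks one of these conditions for at least one endpoint that the list covers.

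At stake is the reading of exploratory tables. A contrast between the two younger onset rows would compare a group with a larger group that contains it. A primary-endpoint table by ICS change would show very large or zero effects that come only from how the rows were formed. A week-48 row for patients without a week-48 value would be blank. None of these tables would inform a reader about effect modification, and the first two could mislead one.

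**Working it through.** **Age of onset.** Take N = 1500 (SAP section 1.3) and let a be the share with onset below 20 and b the share with onset from 20 to 39. The three rows hold Na, N(a + b) and N(1 - a - b) patients, which sum to N(1 + a). The excess Na is the patients counted twice. The documents give no onset distribution, so the shares below are assumptions, with b = 0.30.

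| a | Below 20 | Below 40 | 40 or above | Sum of rows | Share of the below-40 row that is also below 20 |
|---|---|---|---|---|---|
| 0.10 | 150 | 600 | 900 | 1650 | 25% |
| 0.20 | 300 | 750 | 750 | 1800 | 40% |
| 0.30 | 450 | 900 | 600 | 1950 | 50% |

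The size of the overlap depends on the assumption. Its existence does not.

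**Planning inputs.** SAP section 1.3 gives a baseline proportion p1 = 0.40, a change of 5 points (taken as a rise, p2 = 0.45), within-participant correlation r = 0.25, 30% missing at week 48, 80% power and a 0.05 significance level. The alternative in Protocol section 9.1 is two-sided. With (1.960 + 0.842)^2 = 7.849, the pre/post formula that keeps incomplete pairs gives, on the proportion scale:

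n = 7.849 × [0.24 + 0.2475/0.7 - 2 × 0.25 × sqrt(0.24 × 0.2475)] / 0.05^2 = 1481.

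The logit-scale version gives 1476. Both agree with the stated figure of about 1500, so these inputs can be used to illustrate cell sizes.

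**ICS change groups on the primary endpoint.** Assume that change means baseline to week 48 under the endpoint's own prescription rule. The joint probability of ICS at both times is p1p2 + r × sqrt(p1q1p2q2) = 0.18 + 0.25 × 0.2437 = 0.2409. The other cells follow by subtraction: 0.40 - 0.2409 = 0.1591; 0.45 - 0.2409 = 0.2091; and the remainder, 0.3909. Expected week-48 completers are 0.7 × 1500 = 1050.

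| Group | Patients | Baseline | Week 48 | Change (points) |
|---|---|---|---|---|
| With-to-with | 253 | 100% | 100% | 0 |
| With-to-without | 167 | 100% | 0% | -100 |
| Without-to-with | 220 | 0% | 100% | +100 |
| Without-to-without | 410 | 0% | 0% | 0 |

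The weighted sum is (220 - 167)/1050, about +5 points, which is the assumed overall effect restated. Varying r from 0 to 0.75 moves the with-to-with count from 189 to 381 but leaves the last column unchanged. An ordinary logistic model with visit as its only effect has no finite estimate in any row, because the outcome is either constant or perfectly separated by visit; trial fits failed or diverged. If the change were defined at another visit, the baseline value would still be 0% or 100% in every row, so the week-48 change could go in one direction only. The same holds for secondary endpoint 4 (weeks 12, 24 and 36).

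**Reliever change groups.** ICS-formoterol contains an ICS, so a patient prescribed it counts as a yes on the primary endpoint. With change again taken from baseline to week 48:

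- with-to-with is fixed at 100% at both times, a change of 0;
- with-to-without is fixed at 100% at baseline, so the change cannot be positive;
- without-to-with is fixed at 100% at week 48, so the change cannot be negative;
- without-to-without is unconstrained.

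For secondary endpoint 2 at week 48, the grouping is the endpoint's own cross-tabulation, provided that it uses the same rule (SAP section 4.2.2.2). The changes are then 0, -100, +100 and 0 points.

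**Missing at week 48.** SAP section 3.1.4 treats a visit as missing if no assessment falls in its window, and section 3.1.7 does not impute it. This group therefore has no week-48 value and no change to estimate. At the planning rate it would hold 0.30 × 1500 = 450 enrolled patients. They have baseline values and may have values at weeks 12, 24 and 36.

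**The case against.** The strongest reply is that the list is a menu and does not commit anyone to these tables. Both documents qualify it, the analyses are exploratory, and nothing says that every group is crossed with every endpoint. The pairing may also stand in text that is not visible: the exploratory endpoint sections are blank in the public SAP, and SAP section 5 points to subgroups in one of them, 4.2.3.12. Section 5 also plans severe exacerbations by ICS use, so the visible plan already uses an ICS grouping for a different outcome. This stands. A reader might infer that the SAP requires a primary-endpoint effect within each ICS-change group; the documents do not show that. The cell counts themselves are an ordinary and useful transition table.

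On missingness, the protocol states a descriptive purpose, and SAP section 2 declares no change to the protocol's planned analyses. It would therefore go too far to say that the SAP turned this into an efficacy analysis. Nor should the 30% be read as the share of the analysed population. It is a planning assumption, and the FAS requires a post-intervention treatment assessment, so the share there may be lower.

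On age of onset, a reader might conclude that the tables cannot be interpreted at all. That is too strong: each row is a valid description of its own patients, and neither section specifies a test across rows. The overlap is probably a drafting slip.

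The flexible wording nevertheless leaves two things open. It does not make nested onset bands a partition for any endpoint. And it names the primary endpoint without excluding groupings that are uninformative for it. The SAP's amendment history records an August 2024 change meant to specify subgroup definitions and cut-offs, and the current text still has the overlap.

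**Conclusion.** The point holds in a limited form. The firmest part is age of onset. In both documents every patient with onset below 20 falls in two of three rows, so comparisons and interaction tests across those rows would be invalid. This needs no assumption; only the size of the overlap does.

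The ICS-change part is conditional. If change means baseline to week 48 and the table is produced for the primary endpoint, all four results are predetermined. On the same reading, three of the four reliever-change groups are wholly or partly fixed for the primary endpoint, and all four are fixed for secondary endpoint 2 at week 48 if the same prescription rule applies.

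The missing-at-week-48 part is a loss of framing: the group cannot have a week-48 result, and the SAP no longer says that it is there to describe missing data.

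The consequences are confined to exploratory tables. The primary test and the sample size, which the plan's own inputs reproduce, are unaffected. This is a minor point.

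**What to change.** Make three wording changes in SAP section 4.2.4, the first also in Protocol section 9.4.3:

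1. Make the age-of-onset bands non-overlapping, for example below 20, 20 to below 40, and 40 or above, after confirming which cut-points were intended.
2. State that the ICS-containing and ICS-formoterol-reliever change groupings are not used as subgroups for the primary endpoint or for secondary endpoints 2 and 4. Use them only to describe other outcomes, such as ACQ-5 or exacerbations. State the two timepoints that define the change, and label the groups as formed after baseline and not supporting a causal reading.
3. Restore the protocol's framing of the group missing at week 48 as a description of missing data, limited to baseline and earlier-visit values.

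The cost is a text revision and matching table shells. No new data are needed.

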5 INTERIM ANALYSIS

There will be two interim analyses, first interim analyses will mainly focus on the baseline when all subjects enrolled and finish baseline assessment, and the other will happen when all subjects complete week 12 visit.

First interim analysis includes the following parts:

1. Subject disposition
2. Demographics
3. Substance use – nicotine
4. Asthma history
5. Historical asthma exacerbation
6. Prior and concomitant medications – asthma/asthma related comorbidities
7. Prescribed medication – asthma
8. ICS-based maintenance and/or reliever treatment
9. ACQ-5 average scores
10. Distribution of ACQ-5 average scores (Well controlled/Partly controlled/Not well-controlled) and its subgroup listed in Section 4.2.3.12
11. ICS-formoterol as reliever
12. Asthma treatment patterns
13. Numbers of severe asthma exacerbation
 - a. With ICS containing vs. without ICS containing
 - b. Good adherence vs. not
14. Health-related quality of life evaluated by Asthma Quality of Life Questionnaire for 12 years and older (AQLQ(S)+12) score
15. MARS-A average score
16. Hematology

17. Blood Gas
18. IgE
19. FeNO
20. Pulmonary Function Test (PFT)
21. Pulmonary Function Test-Post-BDT (PFT)

Second interim analysis includes the following parts:

1. Subject disposition
2. Demographics
3. Substance use – nicotine
4. Asthma history
5. Historical asthma exacerbation
6. Prior and concomitant medications – asthma/asthma related comorbidities
7. Prescribed medication – asthma
8. ICS-based maintenance and/or reliever treatment
9. ACQ-5 average scores
10. Distribution of ACQ-5 average scores (Well controlled/Partly controlled/Not well-controlled) and its subgroup listed in Section 4.2.3.12
11. ICS-formoterol as reliever
12. Asthma treatment patterns
13. Patient evaluation on whose pulmonologists (whether their pulmonologists develop or review the written asthma action plan and watch the patient using their inhaler, checking their technique)
14. Numbers of severe asthma exacerbation
 - a. With ICS containing vs. without ICS containing
 - b. Good adherence vs. not

15. Health-related quality of life evaluated by Asthma Quality of Life Questionnaire for 12 years and older (AQLQ(S)+12) score
16. MARS-A average score
17. Inhaler skill score of subjects
18. Asthma knowledge score of subjects
19. Patient expectations of asthma treatment
20. Asthma knowledge questionnaire score of investigators
21. Adverse event
22. Hematology
23. IgE
24. FeNO
25. Pulmonary Function Test (PFT)
26. Pulmonary Function Test-Post-BDT (PFT)
27. Branchial Provocation Test

7 APPENDIX

7.1 SAS sample code for proc GLIMMIX

```
proc GLIMMIX data=ics;  
  
class visit (ref='0') hosp doct;  
  
model mpd = visit / dist=binary link=logit oddsratio solution;  
  
contrast 'week 48 vs baseline' time [1,4][-1,5] ;  
  
random subjid hosp doct;  
  
run;
```

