4.2.1.2 Primary Analysis of Primary Endpoint

Proportion of patients with an ICS-based maintenance and/or reliever treatment will be described using the frequency with ICS and corresponding percentage at baseline and week 48.

The primary analysis will use mixed effect logistic regression model, taking the measurement timepoint (baseline/post-baseline) as the fixed effect, hospital, pulmonologist and patient as the random effects. Logit link function will be used, and the model parameters will be estimated by maximum likelihood approach. The compound-symmetry variance-covariance structure will be used. In case of lack of convergency, hospital and prescriber factors will be removed from the model.

Within the framework of this model, first predict for all patients the probability of ICS usage at baseline/ post-baseline and then take the average over baseline/ post-baseline patients to get an estimate of proportion, and finally take the difference between the two proportions as the risk difference estimate, the 95% confidence interval of risk difference in proportion by bootstrapping method will be estimated and presented. Besides, Odds Ratio and P value from the model will also be estimated and presented. The analysis will be performed in FAS. Reference SAS code is shown in section 7.

If medication is taken at least once within 3 months before Visit 0 (week -12), the patients will be regarded as taking this medication at baseline. For Visit 2 (week 12), if medication is taken at least once on or after Visit 1 and on or before Visit 2 (within 3 months before this visit), the subjects will be regarded as taking medications at this visit. For Visit 3 -Visit 5 (week 24, 36 and 48), if medication is taken at least once after last visit and on or before this visit (within 3 months before this visit), the subjects will be regarded as taking medication at this visit.

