7.2 SAS sample code for proc GENMODE

```
proc genmod data=ics;  
  
class subjid hosp doct visit (ref='0')/ param=ref;  
  
model mpd = visit / dist=bin link=logit;  
  
repeated subject=subjid / corr=cs covb corrw;  
  
run;
```

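### The SAP 7.1 reference code does not fit the primary model of SAP 4.2.1.2: it sets up no patient intercepts, requests no likelihood method, and tests an effect that is not in the model

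*SAP*

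**What the plan says.** SAP 4.2.1.2 describes a mixed logistic model, "taking the measurement timepoint (baseline/post-baseline) as the fixed effect, hospital, pulmonologist and patient as the random effects". On estimation it says: "Logit link function will be used, and the model parameters will be estimated by maximum likelihood approach". It adds a compound-symmetry covariance structure. If the model does not converge, only the hospital and prescriber effects are dropped, so the patient effect stays. The risk difference is built from averaged predictions with a bootstrap interval; the odds ratio and p-value come from the model. The section then points to the appendix: "Reference SAS code is shown in section 7".

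The GLIMMIX code in SAP 7.1 has these statements:
- PROC: "proc GLIMMIX data=ics", with no METHOD= option.
- CLASS: "class visit (ref='0') hosp doct".
- MODEL: "model mpd = visit / dist=binary link=logit oddsratio solution".
- CONTRAST: week 48 versus baseline on an effect called `time`, with +1 on level 4 and −1 on level 5.
- RANDOM: "random subjid hosp doct", with no SUBJECT= and no TYPE=.

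The GEE code in SAP 7.2 does declare the patient identifier: "class subjid hosp doct visit (ref='0')/ param=ref".

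**The concern.** The 7.1 code is the SAP's own reference for the primary analysis, and it departs from the model in 4.2.1.2 in three ways. The contrast fault shows itself, because the step cannot deliver the week-48 test. The other two may not. With a numeric ID, a programmer who corrects only the contrast could obtain an odds ratio and p-value from a model that has no patient intercepts and is not fitted by maximum likelihood.

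The sample size relies on the within-patient correlation of 0.25. A fit without patient intercepts gives that up, wholly or in part, in the model standard error. Two analysts working from the same SAP, one from the text and one from the code, could also report different primary odds ratios.

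**Working it through.** **1. Code against text**

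| Element | SAP 4.2.1.2 | SAP 7.1 code |
|---|---|---|
| Patient effect | random effect per patient | subjid in RANDOM, not in CLASS |
| Estimation | maximum likelihood | no method requested |
| Test | week 48 versus baseline | contrast on `time`; model contains only `visit` |
| Timepoint levels | baseline/post-baseline | five implied by the contrast |
| Covariance | compound symmetry | no TYPE= or SUBJECT= |

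A numeric variable outside CLASS enters RANDOM as a regressor with one random coefficient, so no patient has an intercept. A character variable stops the step. With random effects and no METHOD=, GLIMMIX uses residual pseudo-likelihood. These consequences are standard software behaviour; the omissions themselves can be read in the code. To illustrate the second point, I assumed a patient-intercept model matched to the SAP 1.3 inputs. Maximum likelihood gives an odds ratio of 1.31 and residual pseudo-likelihood gives 1.23. I attach no power figure to that point.

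The contrast coefficients are right only if there are exactly five levels with baseline ordered last. Five levels agrees with the five times defined in SAP 4.1.9.

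**2. The plan's sample size reproduces**

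Inputs from SAP 1.3: 40% at baseline, a change of 5 points (taken as 40% to 45%), correlation 0.25, 30% missing at week 48, alpha 0.05 (two-sided per Protocol 9.1), 80% power. On the logit scale:

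n = (1.960 + 0.842)² × [1/0.24 + 1/(0.7 × 0.2475) − 2 × 0.25/√(0.24 × 0.2475)] / 0.2048² = 7.849 × 7.887 / 0.04194 = 1476

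This agrees with approximately 1500, so the sample size is not in question.

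**3. Odds ratio and p-value without patient intercepts**

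Conditions: contrast repaired only, numeric ID, missingness unrelated to baseline, no hospital or pulmonologist variance. On the risk-difference scale with 1500 patients in the FAS, variance × N is:
- true: 0.24 + 0.2475/0.7 − 2 × 0.25 × √(0.24 × 0.2475) = 0.4717, SE 0.01773
- pairing ignored: 0.24 + 0.2475/0.7 = 0.5936, SE 0.01989; ratio 1.122

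Power = Φ((0.05 − 1.96 × SE_model)/SE_true). The FAS needs one post-intervention assessment, so the number contributing a baseline depends on how many of the 450 patients missing at week 48 have an earlier one.

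| Of the 450, kept in FAS | Baseline N / week-48 N | SE ratio | Power with pairing | Power without |
|---|---|---|---|---|
| all | 1500 / 1050 | 1.122 | 80.5% | 73.3% |
| half | 1275 / 1050 | 1.136 | 78.8% | 70.3% |
| none | 1050 / 1050 | 1.155 | 76.4% | 66.1% |

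If hospital and pulmonologist effects absorb 25% or 50% of the covariance (an assumption), the model variance × N at 1500 is 0.5631 or 0.5327, and power is 75.1% or 76.9%.

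**4. Missingness that depends on baseline ICS use (illustration, assumed rates)**

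Take the null at 40%/40% with correlation 0.25. Week-48 ICS use is then 0.40 + 0.25 × 0.60 = 0.55 in baseline users and 0.40 − 0.25 × 0.40 = 0.30 in non-users. Suppose 15% of users and 40% of non-users are missing (30% overall). The observed week-48 proportion is (0.34 × 0.55 + 0.36 × 0.30)/0.70 = 42.1%, a bias of +2.1 points.

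Simulated type I error of the unpaired test (200,000 trials, N = 1500, baseline and week 48 only):
- 2.8% with equal missingness (30%/30%)
- about 5.7–5.9% at 22.5%/35% and 37.5%/25% (bias ±1.1 points)
- 16.2% at 15%/40% and 16.7% at 45%/20% (bias ±2.1 points)

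A patient-intercept maximum likelihood fit to the same two timepoints stays at 5.0–5.1% without bias.

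**The case against.** The strongest defence is that the plan itself is right. The text names the patient effect, the link and maximum likelihood. Protocol 9.4.2.1 agrees on the random effects, and the convergence fallback keeps the patient. The appendix is labelled sample code. Because it cannot run as printed, someone must edit it against the text, and the 7.2 code lists subjid correctly. The bootstrap interval does not use the model SE, so it keeps the pairing if patients or hospitals are resampled. The GEE analysis models patient correlation and would expose a discrepancy.

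All of this stands, and it limits the exposure to the odds ratio and p-value after a partial repair. It does not make the code correct. Only the contrast fault is sure to announce itself, and the documents do not say whether the ID is numeric; Protocol 11.8 says only that it is unique.

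A reader might infer that type I error in this trial would be 16–17%. The documents do not support that. It needs the two most uneven sets of missingness rates, and no section gives such rates. A reader might also infer that patient intercepts remove the bias in any case. That is shown only for a baseline/week-48 fit. With five visits, a single intercept imposes an exchangeable structure, and freedom from bias has not been demonstrated.

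**Conclusion.** The point holds as a mismatch between the SAP's reference code and its own primary model, and it should be fixed. The three defects rest on reading SAP 7.1 against 4.2.1.2 and need none of the calculations.

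The quantified harm is conditional on a contrast-only repair and a numeric ID. Under the conditions of step 3, the model SE is 12–15% too large and 7 to 10 points of power are lost on the odds-ratio test. The loss is smaller if hospital and pulmonologist effects take up part of the correlation. The direction is not guaranteed to be conservative: if missingness depends on baseline ICS use, the estimate can be biased and type I error can exceed 5%, with its size unknown here.

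Two stronger readings are not supported. The specified primary analysis is not wrong, because the text states the right model. The sample size is not undermined, because it reproduces.

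**What to change.** In SAP 7.1:
- Add subjid to CLASS.
- Request a likelihood method, for example METHOD=LAPLACE.
- Specify random intercepts for hospital, pulmonologist and patient, with the patient intercept defined by subjid alone and not nested within pulmonologist. Protocol 6.7 allows patients to see other pulmonologists; nesting would split such a patient into separate intercepts and lose the pairing.
- Write the week 48 versus baseline contrast on `visit`, with coefficients that match the level order.

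In SAP 4.2.1.2, make the timepoint levels and the compound-symmetry sentence agree with the code. It would also help to name ICS use as the modelled event and to state whether the bootstrap resamples patients or hospitals.

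The cost is a short SAP edit and a somewhat longer run time. No new data are needed.
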